##### **MRI: CCMV, FF, and CIMF**

The effect of ACE-083 administered during the open-label extension compared to the treatment administered in the double-blind placebo-controlled phase will be examined for those receiving ACE-083 during the double-blind phase and separately for those receiving placebo during the double-blind phase by comparing the average percent change (left and right side) observed between Day 190 and pre-first treatment baseline (1st 6 months) and Day 358 versus Day 190 (2nd 6 months) using an ANCOVA model.

Covariates to be included into the model are SEQUENCE, CMT-TYPE, and BASELINE where:

- SEQUENCE represents the treatment sequence from double blind to open-label (ACE-083 → ACE-083 or Placebo → ACE-083)
- CMT-TYPE refers to the type of CMT (e.g. CMT1 or CMTX)
- BASELINE represents the baseline TMV from the double-blind period

Least squares estimates of the SEQUENCE effect and 90% confidence intervals will be provided.

If the Day 358 and/or Day 190 assessments have no missing data, then the above ANCOVA model will be used for analysis. If missing data is present, a standard multiple imputation with the above ANCOVA model will be used for analysis as described in [Section 4.11.1](#).

The statistical analysis described above will be done on the Per Protocol Set and will be considered primary. The analyses described above will also be repeated for the Full Analysis Set.

In addition, a line graph of the mean  $\pm$  SEM of the percent change from baseline will be provided by treatment sequence for each scheduled time. For fat fraction, the line graph to be generated will consist of the mean  $\pm$  SEM of the absolute change from baseline by treatment sequence for each scheduled time.

Additional analyses may be performed as appropriate.

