For each pharmacodynamic variable, raw data and changes (percent and/or absolute change) from the start of the open-label extension (Day 190) will be summarized by treatment for each scheduled time using descriptive statistics.

Additional analyses may be performed as appropriate.

Open-label extension vs. double-blind placebo-controlled phase

For each of the following pharmacodynamic variables, a mixed model will be used to assess the effect ACE-083 administered during the open-label extension [Day 358 vs. Day 190 (2nd 6 months)] compared to the effect of the treatment administered in the double-blind placebo-controlled phase [Day 190 vs. pre-first treatment baseline (1st 6 months)] separately for those receiving placebo during the double-blind phase as well as for those receiving ACE-083 during the double-blind phase:

- Percent change in total muscle volume (average of right and left sides) during the openlabel extension vs. double-blind phase
- Percent change in intramuscular fat fraction (average of right and left sides) during the open-label extension vs. double-blind phase
- Percent change in contractile muscle fraction (average of right and left sides) during the open-label extension vs. double-blind phase
- Percent change in contractile muscle volume (average of right and left sides) during the open-label extension vs. double-blind phase

Least squares estimates of this effect and 95% confidence intervals will be provided. In addition, point estimates of this effect and corresponding 95% confidence intervals will be provided for patients having dorsiflexion MRC-MMT grade of 4- to 4+ on both sides.

Additional analyses may be performed as appropriate.

Clinical Study Protocol Study A083-03 Revision: 03 14.2.4.1. Pooled Analyses

If applicable, similar analyses will be performed for pooled Part 1 and 2 data for patients at the same dose level. Pooling by the estimated local dose of ACE-083 in the injected muscle (i.e., mg ACE-083/g muscle) may also be performed. Details of these analyses will be included in the SAP.

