### **Berg Balance Scale**

The effect of ACE-083 administered during the open-label extension compared to the treatment administered in the double-blind placebo-controlled phase will be examined for those receiving ACE-083 during the double-blind phase and separately for those receiving placebo during the double-blind phase by comparing the absolute changes observed between Day 190 and pre-first treatment baseline (1st 6 months) and Day 358 versus Day 190 (2nd 6 months) using an ANCOVA model.

Covariates to be included into the model are SEQUENCE, CMT-TYPE, and BASELINE where:

- SEQUENCE represents the treatment sequence from double blind to open-label (ACE-083  $\rightarrow$  ACE-083 or Placebo  $\rightarrow$  ACE-083)
- CMT-TYPE refers to the type of CMT (e.g. CMT1 or CMTX)
- BASELINE represents the baseline value of the parameter of interest from the double-blind phase

Least squares estimates of the SEQUENCE effect and 90% confidence intervals will be provided.

If the Day 358 and/or Day 190 assessments have no missing data, then the above ANCOVA model will be used for analysis. If missing data is present, a standard multiple imputation with the above ANCOVA model will be used for analysis as described in [Section 4.11.1](#).

The statistical analysis described above will be done on the Per Protocol Set and will be considered primary. The analyses described above will also be repeated for the Full Analysis Set.

In addition, a line graph of the mean  $\pm$  SEM of the absolute change from baseline will be provided by sequence for each scheduled time.

Additional analyses may be performed as appropriate

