#### MRI

Individual MRI data will be listed.

For each MRI variable, the raw data as well as the absolute and percent change from baseline will be summarized by cohort for each scheduled time and side treated [left and right]. The average absolute and percent change [from left and right sides] will also be provided.

For total muscle volume, calculated contractile muscle volume, fat fraction, and calculated intramuscular fat, least squares estimates of the effect of ACE-083 and corresponding 90% and 95% confidence intervals will be produced for the average percent change data at Day 106 [from left and right sides] (absolute change for fat fraction at Day 106) using an ANCOVA with BASELINE, COHORT, and BASELINE\*COHORT as variables where:

- COHORT represents the dose level of ACE-083 administered to the muscle
- BASELINE represents the baseline value of the parameter of interest
- BASELINE\*COHORT represents the interaction of baseline and cohort

Graphical summaries of the mean  $\pm$  SEM will be provided for each cohort and scheduled time.

Additional analyses may be performed as appropriate.

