### **MRI: Calculated Contractile Muscle Volume (CCMV), Fat Fraction (FF), and Calculated Intramuscular Fat (CIMV)**

Individual data will be listed.

Descriptive statistics will be provided by treatment group and scheduled time for raw data and changes from baseline (absolute and percent change) for each side [left and right]. The average absolute and average of the percent change for the left and right sides will also be provided.

An ANCOVA model will be fitted in order to assess the effect of ACE-083 on the Day 190 average of left and right side percent change (absolute change for FF) from baseline. Covariates to be included in the model are TREATMENT, BASELINE, and CMT-TYPE where:

- TREATMENT represents the treatment group (ACE-083 or placebo)
- BASELINE represents the baseline parameter of interest (average of left and right sides)
- CMT-TYPE refers to the type of CMT (e.g. CMT1 or CMTX)

For each of the selected MRI parameters, the effect of ACE-083 on the Day 190 average percent change (absolute change for FF) from baseline will be estimated using the ANCOVA model described above and tested using a 0.1 significance level (2-sided). The least-square mean estimate along with the corresponding 90% confidence interval will be provided. In addition, the

95% confidence interval will also be provided as well as a bar chart of the least squares mean estimates ( $\pm$  SEM) for each of the treatment groups.

If the Day 190 selected MRI parameter has no missing data, then the above ANCOVA model will be used for analysis. If missing data is present, a standard multiple imputation with the above ANCOVA model will be used for analysis as described in [Section 4.11.1](#).

A mixed model repeated measures (MMRM) analysis will be performed to assess the sensitivity to the ANCOVA analysis described above. An unstructured covariance structure will be used to model the within-patient covariance across visits. Other covariance structures will be considered if the unstructured covariance fails. The covariates to be included consist of all of the covariates described above for the ANCOVA with the addition of the following additional covariates: VISIT where VISIT represents the scheduled visit day post first dose of MRI assessment and TREATMENT\*VISIT.

Similar to what was described for the ANCOVA analysis above, if missing data is present, a standard multiple imputation with the above MMRM model will be used for analysis as described in [Section 4.11.1](#).

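### The SAP's open-label versus double-blind model adjusts CCMV, fat fraction and CIMF for baseline total muscle volume instead of each parameter's own baseline, and its fat-fraction estimate is on a different scale from the double-blind one.

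*SAP*

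**What the plan says.** The section at issue is SAP 4.8.2.2.3, under MRI: CCMV, FF, and CIMF. It sets the change over the first six months against the change over the second six months, by "comparing the average percent change (left and right side) observed between Day 190 and pre-first treatment baseline" and the corresponding change from Day 190 to Day 358. The model is an ANCOVA with SEQUENCE, CMT-TYPE and BASELINE. For all three parameters, "BASELINE represents the baseline TMV from the double-blind period". The output is least squares estimates of the sequence effect with 90% confidence intervals. The response is percent change, with no exception for FF. The section's graph does make an exception: "For fat fraction, the line graph to be generated will consist of the mean" absolute change by sequence.

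The double-blind model for the same parameters, SAP 4.8.2.2.1, differs on both counts. Its response is the "average of left and right side percent change (absolute change for FF) from baseline", and its covariate is the parameter's own: "BASELINE represents the baseline parameter of interest (average of left and right sides").

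The protocol (14.2.4, open-label extension versus double-blind phase) lists for this comparison: "Percent change in intramuscular fat fraction (average of right and left sides) during the open-label extension vs. double-blind phase". It names no covariates for that model.

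**The concern.** Two things in the section do not fit the rest of the plan.

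The first is the covariate. Adjusting for the baseline of the outcome removes chance differences between the sequences in that baseline and usually narrows the interval. Adjusting FF for muscle volume does this only as far as muscle volume and FF happen to be related. With about 20 patients per sequence, chance imbalance is a practical matter. Because the protocol names no covariates here, a programmer has only the SAP line to follow, and following it literally puts TMV into all three models.

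The second is the FF scale. The randomised FF comparison will be in percentage points and the open-label comparison in percent of the starting value, and the graph beside the latter will be in percentage points again. A reader of the report cannot set the two FF estimates next to each other without a further calculation.

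**Working it through.** **Covariate: the parallel sections side by side.**

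| Analysis | Outcome | BASELINE |
|---|---|---|
| SAP 4.8.2.2.3, MRI: TMV | TMV | baseline TMV |
| SAP 4.8.2.2.3, MRI: CCMV, FF, and CIMF | CCMV, FF, CIMF | baseline TMV |
| SAP 4.8.2.2.1, same three parameters, double-blind | CCMV, FF, CIMF | parameter of interest |
| SAP 4.8.2.1, Part 1 MRI | TMV, CCMV, FF, fat volume | parameter of interest |
| SAP 4.7.2.2.3, 10-meter walk/run, 6-minute walk, Berg, CMT-HI, CMTES2 | each parameter | parameter of interest |
| SAP 4.7.2.2.3, MVIC and MRC-MMT | each parameter | baseline value from the double-blind phase |

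The Berg section shows the usual form: "BASELINE represents the baseline value of the parameter of interest". Only the second row pairs an outcome with another variable's baseline. Its wording is identical to that of the first row, the section immediately before it. SAP Section 5 gives no reason for it. Carried-over text is the likely explanation.

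**How far TMV can stand in for each baseline.** SAP 4.8.1.1 defines CCMV = TMV × (100 − FF)/100 and calculated intramuscular fat volume = TMV × FF/100. Take two patients with the same TMV and assumed baseline FF of 10% and 20%:
- CCMV is 90% and 80% of TMV, a ratio of 90/80 = 1.125.
- Calculated fat volume is 10% and 20% of TMV, a ratio of 2.
- FF itself differs by a ratio of 2.

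The model as written gives both patients the same baseline. TMV is thus a fair proxy for CCMV, a poorer one for fat volume, and no part of the FF value as such. The problem is greatest for FF.

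**Precision.** The section states no figure to reproduce, so this is an illustration. Assumptions: one response per patient with SD 10 (borrowed from the TMV sample-size text), 18 patients per sequence, and correlation r between covariate and response. Half-width of the 90% interval = t(0.95; 32 df) × 10 × √(1 − r²) × √(2/18).

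| r | residual SD | half-width |
|---|---|---|
| 0 | 10.00 | 5.65 |
| 0.3 | 9.54 | 5.39 |
| 0.5 | 8.66 | 4.89 |
| 0.7 | 7.14 | 4.03 |

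The loss is the gap between the row for TMV and the row for the parameter's own baseline. The documents give neither correlation.

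**FF scale.**
- Part 1 (SAP 4.8.2.1): "absolute change for fat fraction at Day 106".
- Double-blind (SAP 4.8.2.2.1): absolute change.
- Open-label versus double-blind (SAP 4.8.2.2.3): percent change in the model, absolute change in the graph.
- Protocol 14.2.4: percent change for both the double-blind model and the open-label comparison.
- Protocol endpoints (Section 4): percent and absolute change.

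The scales are not interchangeable. At assumed baselines of 5, 10, 20 and 40%, a 2-point fall is −2/5 = −40%, −2/10 = −20%, −2/20 = −10% and −2/40 = −5%. The denominator also moves between periods: FF going from 20 to 18 to 16 is −2 points each time, but −2/20 = −10% and then −2/18 = −11.1%.

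**Sample size, to confirm that it is untouched.** Two-sided alpha 0.10, 90% power, difference 10, SD 10: n = 2 × (1.645 + 1.282)² × (10/10)² = 17.1, so 18 per arm. The t-test power at 18 is 0.902, and 36/0.9 = 40. The SAP's 36 and 40 reproduce, and they concern TMV only.

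**The case against.** A reader might infer that percent change is the wrong scale for FF and that this section is the one in error. The documents do not support that. The protocol specifies percent change for this very comparison and lists both scales as endpoints, and the subgroup list in SAP 4.9 uses both. The section that departs from the protocol is the double-blind model in SAP 4.8.2.2.1, and SAP Section 5 does not list that departure. Replacing percent change with absolute change here would add a second one.

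A reader might also infer that the two six-month periods cannot be compared. They can: within SAP 4.8.2.2.3 both are expressed as percent change. The mismatch is only with the separate double-blind estimate and with the section's own graph. The graph is descriptive and shows a legitimate endpoint scale, and descriptive statistics for FF are planned on both scales in both periods, so the material for a common-scale reading will exist. Nor does the section name a hypothesis test; it plans estimates and intervals.

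On the covariate, the best defence is that TMV enters the formulas for CCMV and calculated fat volume, so the three parameters are not equally affected, and that the harm cannot be sized from the documents. Both points stand. They limit the size of the problem but give no reason to prefer TMV, and they do not help for FF.

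**Conclusion.** The covariate definition in SAP 4.8.2.2.3 for CCMV, FF and CIMF is out of line with the SAP's double-blind model for the same parameters and with the sibling open-label comparisons, and it should be corrected. Followed literally, it leaves imbalance in each parameter's own baseline not directly adjusted, most clearly for FF. The precision cost runs from nothing, if TMV predicts as well as the parameter's own baseline, to 5.65 versus 4.89 in half-width if TMV predicts nothing and the own baseline has correlation 0.5, under the assumed SD and group size. That it is carried-over text is an inference from the identical wording.

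The FF scale is a narrower matter. The open-label estimate follows the protocol but cannot be read directly against the double-blind estimate, and the double-blind model's change of scale is unrecorded. The documents do not establish either scale as the right one.

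This is a supportive estimation analysis that draws on uncontrolled open-label data. The primary TMV analysis and the sample size are unaffected.

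**What to change.** 1. In SAP 4.8.2.2.3, MRI: CCMV, FF, and CIMF, define BASELINE as the double-blind baseline value of the parameter of interest. This is one phrase.
2. In the same section, report the FF estimate and its 90% interval on both percent and absolute change. Percent change keeps to the protocol; absolute change lets the estimate be set beside the double-blind one and matches the planned graph. This is one phrase and one extra model run.
3. In SAP Section 5, record that the double-blind FF model uses absolute change where Protocol 14.2.4 specifies percent change. This is one list entry.

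No new data, visits or patients are needed. All three edits should be made before database lock and unblinding.

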### **MRI: Other Parameters**

Descriptive statistics will be provided by sequence where sequence represents the treatment sequence from double-blind to open-label (ACE-083  $\rightarrow$  ACE-083 or Placebo  $\rightarrow$  ACE-083) for the comparison of the percent change observed between Day 190 and pre-first treatment baseline (1st 6 months) and Day 358 versus Day 190 (2nd 6 months).

Additional analyses may be performed as appropriate.

## **4.9. Subgroup Analyses**

Subgroup analyses will be performed for selected efficacy and pharmacodynamics data from the double-blind period of Part 2.

Subgroups consist of the following:

- Ankle Dorsiflexion MRC-MMT Grade {weaker of two sides at Screening}: (3 to 4-; 4 to 4+)
- Ankle Dorsiflexion Screening MRC-MMT Grade of 4- to 4+ on both left and right sides
- Plantar Flexion MRC-MMT Grade {weaker of two sides at Screening}: (4- to 4+; 5- to 5)
- Knee Extension MRC-MMT Grade {weaker of two sides at Screening}: (3+ to 4+; 5- to 5)
- MRC-MMT Grade {weaker of two sides at Screening} for plantar flexion and knee extension
  - Levels are “Both 5- to 5” and “Not both 5- to 5”.
  - “Both 5- to 5” means that the MRC-MMT grade {weaker of two sides} for both plantar flexion and knee extension must both be between 5- and 5.

- “Not both 5- to 5+” means that the MRC-MMT grade {weaker of two sides} for any or both plantar flexion and knee extension should not both be between 5- and 5+. For example, a patient with plantar flexion MRC-MMT grade {weaker of two sides} of a 5- and knee extension MRC-MMT grade {weaker of two sides} of 4 would be classified as “Not both 5- to 5+”.
- Baseline Fat Fraction (%): (< median;  $\geq$  median)
- CMT type: (CMT1, CMTX)
- CMT gene mutation: (CMT1A, not CMT1A)
- Usage of Braces (Yes; No)
  - This information is contained in the individual patient’s CMT disease history
- Dose per Calculated Contractile Muscle Mass (mg/g): (< median;  $\geq$  median)
- Exercise Program: (resistance; no resistance)
  - The “resistance” subgroup includes patients who responded “Yes” to the question “Does the patient have a regular (at least once a week) exercise program?” and reported “Resistance training” as a type of exercise program.
  - The “no resistance” subgroup includes patients who responded “Yes” to the question “Does the patient have a regular (at least once a week) exercise program?” and did not report “Resistance training” as a type of exercise program.
- Baseline CMT-HI Total Score: (< median;  $\geq$  median)
- Activity level (steps/d): (< median;  $\geq$  median)
  - This is defined as the average number of steps per day as measured by the PAMSys™ device over the patient’s study participation in the Part 2 double-blind period, adjusted for overall compliance in using the device to record such activity.
- ADA (ADA +; ADA-)
  - ADA+ means that the patient had positive ADA for ACE-083 at least once during the double-blind period of Part 2
  - ADA- means that the patient did not have positive ADA for ACE-083 at least once during the double-blind period of Part 2

Subgroup analyses will be performed for the following parameters:

- Day 190 average percent change in total muscle volume from baseline
- Day 190 average percent change in calculated contractile muscle volume from baseline
- Day 190 average absolute change in fat fraction from baseline
- Day 190 average percent change in fat fraction from baseline
- Day 190 average percent change in ankle dorsiflexion MVIC from baseline

- Day 190 average absolute change in ankle dorsiflexion MMT-MRC decimal score from baseline
- Day 190 percent change in 6MWD from baseline
- Day 190 percent change in time to complete 10mW/R from baseline
- Day 190 absolute change in CMT-HI total score from baseline
- Day 190 absolute change in CMT-HI foot/ankle strength subscale score from baseline
- Day 190 absolute change in CMT-HI balance subscale score from baseline
- Day 190 absolute change in CMT-HI fatigue subscale score from baseline
- Day 190 absolute change in CMT-HI mobility subscale score from baseline
- Day 190 absolute change in CMT-HI activities subscale score from baseline
- Fall risk reduction during double-blind period

Subgroup analyses will be performed using similar ANCOVA models described in previous sections for each subgroup category provided that the sample size is at least 4. Because of the reduced sample size within each subgroup category, it is not planned to include CMT-TYPE into such models. For each subgroup category, the treatment effect will be estimated and tested using a 0.1 (two-sided) significance level with the corresponding 90% confidence interval. Bar charts of the least squares mean estimates ( $\pm$  SEM) for each of the treatment groups will be provided.

For purposes of this study, findings of subgroup analyses are considered to yield hypothesis generating statements for future study. It is not planned to control the overall type-1 error.

Additional analyses may be performed as appropriate.

Data from multiple imputations described in [Section 4.7.2.2.1](#) will be used.

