11. STUDY DRUG MATERIALS AND MANAGEMENT

11.1. Study Drug

Study drug is either ACE-083 or placebo. ACE-083 is a recombinant fusion protein consisting of a modified form of human follistatin linked to a human IgG2 Fc domain. Placebo will be sterile normal saline (0.9% sodium chloride for injection).

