¹ Study procedures must be done prior to administration of study drug. Reference the Study Manual for the order of study procedures. Laboratory samples and functional/strength assessments may be collected up to 24 hours prior to administration of study drug. All visit-day windows should be considered relative to the date of the previous dose of ACE-083. Actual visit days (e.g., Day 1, Day 8, Day 22) may be different than planned due to windows on visits and potential dosing delays. Time of study drug administration is the time of the first injection.

² Patients who discontinue prior to the Day 358/ET visit should complete the Day 358/ET visit at the time of discontinuation and return for the remaining follow-up period visit. If an MRI has been completed within 4 weeks of discontinuation, it does not need to be repeated as part of the Day 358/ET visit procedures.

³ Pregnancy test for women of childbearing potential to be performed and negative result confirmed before dosing.

⁴ Includes knee extension, ankle dorsiflexion, and ankle plantarflexion.

⁵ To be performed at screening if patient has not already had testing performed previously.

⁶ Full physical examination includes skin, head, eyes, ears, nose, throat and neck, lymph nodes, cardiovascular, respiratory, gastrointestinal, musculoskeletal, and neurological

⁷ Limited physical examination includes skin, cardiovascular, respiratory, musculoskeletal and neurological assessments

⁸ Injection site examination including but not limited to evaluating erythema, pain, bruising, bleeding, and other signs of discomfort or skin reaction to be completed at least 30 minutes after injection.

⁹ Vital signs (weight, heart rate, systolic and diastolic blood pressure) must be taken prior to administration of study drug on dosing days. Height is collected only at screening.

¹⁰ Tests defined in Appendix 2, Table 7.

¹¹ Including but not limited to: insulin-like growth factor-1 (IGF-1) and serum C-terminal collagen crosslinks (CTX)

¹² If a patient has a positive ADA result at Day 393/EOS, the patient will be asked to return to the clinical site for additional follow-up approximately every 3 months until a negative or stable result is obtained.

¹³ PK samples on a dosing day have a ±15 minute window for post-dose sample collection, based on the time of the first injection. Pre-dose samples may be collected up to 4 hours prior to dosing.

¹⁴ ECG is to be conducted ± 1 hour of the 4h PK sample.

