**Table 1: Planned Doses to be Administered for Part 1**

Cohort	Dosing Days	Muscle	Planned Dose Level	Type of Administration	ACE-083 n
1	1, 22, 43, 64, and 85	Tibialis Anterior	150 mg	Bilateral	6
2	1, 22, 43, 64, and 85	Tibialis Anterior	200 mg	Bilateral	6
3	1, 22, 43, 64, and 85	Tibialis Anterior	240 mg	Bilateral	6
Total Number of Patients (Planned)					18

Periodic reviews of selected blinded safety and imaging data will be reviewed by the Safety Review Team (SRT) in accordance with the SRT Guidelines.

#### 3.2. Part 2

Prior to the initiation of Part 2, a review of the safety and efficacy data from Part 1 will be done in order to determine the recommended dose level. Up to 40 patients will be enrolled and randomized (1:1 ratio) to receive either ACE-083 (n=20) or placebo (n=20) bilaterally. Patients will receive study drug once every three weeks for approximately 6 months (9 doses). If a patient discontinues the study for reasons other than a safety issue related to investigational study drug and the patient had not completed the Day 43 visit, the patient may be replaced. The replacement patient will receive the same treatment as the patient replaced.

Patients who complete the double-blind treatment period will immediately roll over to open-label treatment with ACE-083. All patients will receive ACE-083 administered at the same dose as in the double-blind period. They will receive bilateral injections, once every three weeks for approximately 6 months (8 doses). In Part 2, the SRT will periodically review the blinded safety data.

A stratified randomization schedule will be prepared under the direction of the Sponsor with the stratification factor of “CMT disease type” (values are CMT1 and CMTX). Because Part 2 is multicenter, an Interactive Response Technology (IRT) system will be used to randomize patients sequentially across clinical sites.

Similar to Part 1, periodic reviews of selected blinded safety and imaging data will be reviewed. Further details concerning the frequency and timing of SRT reviews of Part 2 data are described in the SRT Guidelines.

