  - Summaries will be provided for each side (left and right) separately for ankle dorsiflexion, knee extension, and plantar flexion.
  - MRC-MMT grades will also be summarized (frequency with percent) by the weakest grade (left or right) for ankle dorsiflexion, knee extension, and plantar flexion.
  - MRC-MMT SCORE which represents the conversion of the MRC-MMT grade to the decimal version as follows: 5 = 5.0, 5- = 4.67, 4+ = 4.33, 4 = 4.0, 4- = 3.67, 3+ = 3.33, 3 = 3.0, 3- = 2.67, 2+ = 2.33, 2 = 2.0, 2- = 1.67, 1+ = 1.33, 1 = 1.0.
    - This will be determined for each side (left and right) and then averaged. The average will be presented in the summary table. This will be done for ankle dorsiflexion.
- Dose of ACE-083 expressed as (mg/g calculated total muscle mass)
- Dose of ACE-083 expressed as (mg/g calculated contractile muscle mass)

- CMTES2 Score
  - See [Section 4.7.1.4](#) for details on how this score is derived.
- Berg Balance Scale total score
  - See Section 4.7.1.4 for details on how this score is derived.

The table below outlines how to derive the dose of ACE-083 expressed as either mg/g total muscle, or mg/g contractile muscle:

	Dose of ACE-083 Expressed as	
	mg/g Calculated Total Muscle Mass	mg/g Calculated Contractile Muscle Mass
Bilateral Cohorts	
Step 1: For each side (right and left), compute the following: Dose injected (mg) / (Baseline CCMV {mm^3} * [1.06/1000] + Baseline CIMFV {mm^3} * [0.9/1000])
 
Step 2: Compute average of the Dose of ACE-083 expressed as mg/g total muscle for each side using the information obtained from Step 1.
	
Step 1: For each side (right and left), compute the following: Dose injected (mg) / (Baseline CCMV {mm^3} * [1.06/1000])
 
Step 2: Compute average of the Dose of ACE-083 expressed as mg/g contractile muscle for each side using the information obtained from Step 1.

CCMV = Calculated contractile muscle volume; CIMFV = Calculated intramuscular fat volume

This data will be summarized using appropriate descriptive statistics.

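### SAP 4.9 tests ACE-083 against placebo within halves of ACE-083 dose per gram of contractile muscle with no rule for classing placebo patients, and within ADA groups defined after randomisation

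*SAP*

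**What the plan says.** SAP 4.9 lists 14 subgroup factors and 15 outcome parameters for the Part 2 double-blind period. It requires a contrast in all of them: "For each subgroup category, the treatment effect will be estimated and tested using a 0.1 (two-sided) significance level". Two factors matter here.

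- **Local dose.** The factor is "Dose per Calculated Contractile Muscle Mass (mg/g", cut at a median; the section does not say whose. The variable is defined only in the derivation table of SAP 4.4.2, as a dose of ACE-083: "For each side (right and left), compute the following: Dose injected (mg", over that side's baseline calculated contractile muscle mass, with the two sides then averaged. Protocol 11.1 says of the control: "Placebo will be sterile normal saline (0.9% sodium chloride for injection". I found no value or class for placebo patients in SAP 4.1.5, 4.4.2, 4.9 or 5, or in the protocol.
- **ADA.** The definition is "ADA+ means that the patient had positive ADA for ACE-083 at least once during the double-blind period of Part 2"; ADA- is the complement.

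A category is analysed if its sample size is at least 4. The SAP does not say whether that is per category or per arm. SAP 4.9 also says that subgroup findings are hypothesis generating and that overall type 1 error is not controlled.

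**The concern.** A treatment effect within a subgroup needs both arms in that subgroup, and membership that treatment does not influence. The dose factor fails the first condition if its formula is applied as printed, because the formula has no meaningful value in the placebo arm. Someone must then choose a placebo rule and a median after the plan is final, which is the discretion a SAP is meant to remove. The ADA factor fails the second condition: antibodies to ACE-083 arise largely from receiving it, so conditioning on them selects patients differently in the two arms. At stake is whether these exploratory rows can be produced and interpreted. The main result is not at stake.

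**Working it through.** **Background figure.** The plan gives no figure for these subgroups. Its sample size is not in dispute and reproduces. With a difference of 10, SD 10 and two-sided alpha 0.10, the noncentrality at 18 per arm is 10 / (10 × √(2/18)) = 3.0, and t-test power is 90.2%. Allowing for dropout, 36 / 0.90 = 40.

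**Dose split, literal formula.** Inputs are the planned arm sizes (20 and 20 randomised, 18 and 18 evaluable), placebo at 0 mg/g or undefined, and any ACE-083 value above 0. No muscle-mass distribution is needed. The planned rows are 2 halves × 15 parameters = 30.

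| Reading | Below median (placebo/active) | At or above median (placebo/active) | Rows with no usable contrast |
|---|---|---|---|
| Placebo 0, pooled median, 20 vs 20 | 20/0 | 0/20 | 30 |
| Placebo 0, pooled median, 18 vs 18 | 18/0 | 0/18 | 30 |
| Placebo 0, pooled median, 18 placebo vs 20 active | 18/1 | 0/19 | 15 |
| Placebo 0, pooled median, 20 placebo vs 18 active | 0/0 | 20/18 | 15 |
| Placebo 0, ACE-083-arm median, 20 vs 20 | 20/10 | 0/10 | 15 |
| Placebo undefined | no placebo | no placebo | 30 |

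In the fourth row the 19th and 20th of 38 ordered values are both 0, so the median is 0: the lower half is empty and the upper half is the whole sample.

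**Dose split, nominal dose.** Give every patient the single planned Part 2 dose D. The value is D × (1/left mass + 1/right mass) / 2. D cancels from the ranking, so both arms are classed by baseline mass alone. At 20 vs 20 with one pooled median, the placebo count in a half is hypergeometric:

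- chance of a one-arm half: 2 / C(40,20) = 1.5 × 10⁻¹¹;
- chance that any arm-by-half cell falls below 5: 0.04% (0.2% at 18 vs 18).

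No rows are lost. Each half has about 10 per arm. There the noncentrality is 10 / (10 × √(2/10)) = 2.24, and power for the planned 10-point difference is about 69%.

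A split on average baseline mass is close to this but not identical when the sides differ. Sides of 20 and 60 g (average 40 g) give 0.0333 × D, while 35 and 35 g give 0.0286 × D. The heavier pair has the larger dose per gram.

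**ADA split.** The documents give no ADA rates, so all rates here are assumptions.

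- The chance that ADA+ holds no placebo patient among 20 is (1 − p)²⁰: 100%, 82%, 67%, 36% and 12% for placebo positivity p of 0%, 1%, 2%, 5% and 10%.
- With ACE-083-arm positivity of 20%, 50% or 80%, active patients alone reach 4 in ADA+ with probability 59%, 99.9% or about 100%. A per-category reading of the minimum would therefore often pass a group with few or no placebo patients.
- At those rates ADA- retains an expected 16, 10 or 4 of the 20 active patients, set against nearly all of the placebo arm if placebo positivity is low.

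**The case against.** **The row losses depend on the reading.** The derivation sits under baseline characteristics, its denominator exists in both arms, and SAP 3.2 says of the extension: "All patients will receive ACE-083 administered at the same dose as in the double-blind period". A nominal value is easy to compute and loses nothing. Another possible rule, comparing each active half with the whole placebo arm, would give 10 vs 20 twice, though not balanced on muscle mass. This stands as far as it goes: a reader might infer that the analysis cannot be run or must lose 15 or 30 rows, and the documents do not support that. But neither rule is written, and the formula that is written says dose injected.

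**The section is only hypothesis generating, and a missing arm would show in the output.** Both points are true, and they limit the impact. The label deals with multiplicity; it does not supply a comparator.

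**The size of the ADA problem is assumed.** This also stands. If few ACE-083 patients become positive, ADA- is nearly the whole trial and selection is slight. Nor can one infer that placebo patients are never ADA+: Protocol Table 6 schedules a Day 1 ADA sample, and its footnote says "Study procedures must be done prior to administration of study drug", so pre-existing or false-positive reactivity could be recorded. What remains is that the status depends on exposure, whatever its frequency.

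**Two further inferences should not be drawn.** Protocol 14.2.4.1 allows pooling of Parts 1 and 2 by local dose, but that is a separate optional analysis, untouched by this omission. The activity subgroup averages steps over the double-blind period, but it is biased only if treatment changes steps, on which the documents are silent.

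**Conclusion.** The point holds as an unstated rule and an exposure-dependent split, with minor impact. Read literally, the dose-per-mass factor leaves at least one half without a usable comparison; this needs no assumption beyond the formula, the saline control and the planned arm sizes. It is conditional on that reading, since an unstated nominal-dose rule would avoid it. ACE-083 against placebo within ADA+ or ADA- compares groups formed by post-randomisation status. Its direction and size cannot be determined from the documents. A reader might infer that the primary analysis or sample size is compromised; neither is, because neither uses these subgroups.

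**What to change.** Amend SAP 4.9 before unblinding.

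- **Dose per mass.** For the test against placebo, class both arms by a baseline quantity available in both: baseline calculated contractile muscle mass, or the SAP 4.4.2 steps with the planned Part 2 dose as a nominal dose. Name one, and use one median pooled over both arms. State the downside: this is a baseline-mass split, not an actual-dose split, and it ignores any dose reductions, which Protocol 10.1.1 permits. To keep the local-exposure question, report outcome by actual mg/g descriptively within the ACE-083 arm.
- **ADA.** Replace the treatment tests with a descriptive summary by ADA status within the ACE-083 arm, labelled non-randomised.
- **Minimum size.** Test a category only when both arms are present, and say whether the minimum of 4 is per arm.
- **Activity.** Label this split as post-randomisation; nothing more is needed.

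The cost is a few sentences and small programming changes, with no new data. The 2 × 15 = 30 ADA rows would be described instead of tested.
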